3.1.2 Up-dosing (Group 1 Only)

Subjects will receive AR101 starting at a dose of 3 mg once daily and gradually escalating every 2 weeks to a maximum of 300 mg once daily, according to the Up-dosing Maintenance

Schedule ([Table 2](#)). All escalation doses will be administered under direct observation; subsequent doses will be dispensed to the subject/guardian and administered at home. Doses may be adjusted for tolerability or intercurrent illness; the Up-dosing period may thereby be extended to a maximum of 40 weeks. Subjects unable to escalate to 300 mg within 40 weeks will be considered escalation failures for analysis purposes. Subjects able to escalate to 300 mg and maintain this dose regimen for 2 weeks will have completed Up-Dosing and will enter the Maintenance Period.

Table 2: Up-dosing Maintenance Schedule (Group 1 Subjects Only)

Up-dosing and Maintenance Schedule (Group 1 only)			
Dose Number	AR101 Dose, mg	Interval (weeks)	Percent Increase from previous dose
1	3	2 ^a	n/a
2	6	2	100
3	12	2	100
4	20	2	67
5	40	2	100
6	80	2	100
7	120	2	50
8	160	2	33
9	200	2	25
10	240	2	20
11	300	2	25

^a Interval includes Day 2 of Initial Escalation.

n/a = not applicable.

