4.3 Early Termination

4.3.1 Criteria for Early Termination

Any subject will be prematurely terminated from additional study drug treatment and excluded from any further study procedures (except for safety follow-up) for any one of the following reasons:

1. Life-threatening symptoms (Consortium of Food Allergy Research [CoFAR] Grade 4; refer to [Appendix 4](#)), including, but not limited to, anaphylaxis resulting in hypotension, neurological compromise, or mechanical ventilation secondary to peanut OIT dosing or any peanut food challenge
2. Severe allergic hypersensitivity symptoms (CoFAR Grade 3; refer to [Appendix 4](#)), including, but not limited to, those that require intensive therapy (to be determined by the investigator, but may include such interventions as intravenous (IV) epinephrine, intubation, or admission to an intensive care unit) or those that are recurrent. Subjects who experience severe symptoms (eg, severe nausea, rhinorrhea, or pruritus) that are not life-threatening, not requiring intensive therapy, and not associated with any other features indicating a serious clinical condition, and who the Investigator feels are suitable to continue with the study, will be discussed with the Medical Monitor and may continue the trial under close supervision, if both the Investigator and the Medical Monitor deem it appropriately safe to do so.
3. Pregnancy
4. Non-adherence (non-compliance) with study product dosing, as indicated by missing ≥ 7 consecutive dosing days on any 1 occasion, or 3 consecutive dosing days on 3 or more occasions during the Up-dosing Period, as this could constitute a potential safety issue (QD regimens only)
5. Medically indicated circumstances (eg, as part of the treatment for intercurrent AEs) that require missed study product dosing for >14 consecutive days, except for the voluntary 30-day hiatus for AEs occurring at or before the 20-mg dose (Group 1 only)
6. The subject elects to withdraw consent from all future study activities, including follow-up.
7. The subject is “lost to follow-up” (ie, no further follow-up is possible because attempts to reestablish contact with the subject have failed).
8. The subject’s continued participation in the study is assessed by the investigator to constitute a threat to the safety of the subject or the safe conduct of the study.
9. The subject dies (CoFAR Grade 5).

10. Poor control or persistent activation of secondary atopic disease (eg, atopic dermatitis, asthma)

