6.5.3.2 Assessment of Chronic/Recurrent Symptoms

Gastrointestinal symptoms were the most common potentially allergic symptoms to occur on a subacute, chronic, and/or recurrent basis during Phase 2 clinical trials with AR101. Atopic dermatitis, seasonal allergies, or asthma are other potentially non-acute allergic reactions that could be brought on or exacerbated by OIT. The absence of a clear temporal relationship between dosing and the emergence of recurrent symptoms may help to distinguish these from acute dosing-related symptoms.

If symptoms arise that suggest a chronic/recurrent reaction to study product in a daily dosing regimen, the dose level should be reduced. As with acute symptoms, the level of the dose reduction should be guided by the severity of the symptoms. Symptomatic treatment is permitted ([Section 6.5.5](#)), but should be used as a supplement to dose reduction, not a substitute for it.

For chronic/recurrent GI symptoms, especially upper GI symptoms, investigators are advised to have a low threshold for instituting a dose reduction and/or for considering early discontinuation of affected subjects from the study, owing to the potential for EoE. When dose interruptions occur due to GI AEs, the subject should fill out a PEESS v 2.0 questionnaire as soon as possible ([Section 7.3.3.2](#)). Voluntary saliva collection should also ensue as per [Appendix 6](#) for all subjects consented into this additional study. Any subject who has not consented for participation into the voluntary saliva study, and who experiences GI AEs that interrupt dosing, may be approached to provide consent and donate saliva at the time of their dosing interruption and/or withdrawal.

For Group 1 subjects determined to be having dose-limiting chronic/recurrent GI symptoms during Up-dosing, at up to and including the 20 mg/d dose level, it is advised that dosing of study product be suspended for 4 weeks and resumed at a dose level of 3 mg/day for a minimum of 4 weeks, with the first dose given in the CRC under medical supervision. If tolerated, up-dosing may resume, with caution, according to the usual schedule, as tolerated. (Note: The 4-week suspension of dosing in response to chronic/recurrent GI symptoms occurring up to and including the 20 mg/d level is the only protocol-specified exception to the rules for missed OIT delineated in [Section 6.6](#)).

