- Return to the CRC for dosing of a previously tolerated dose level, either a 1- or 2-step reduction (per investigator judgment, based on severity of reaction) and follow the procedures described in [Section 6.5.5.2](#) above.
- Institute the 4-week hiatus from dosing, with resumption of dosing at the 3 mg/d dose level, as permitted for recurrent GI symptoms occurring at or before the 20-mg dose, as described in [Section 6.5.3.2](#).
- Discontinuation of dosing.

[figure not shown]
Any subject who discontinues up-dosing due to severe or repeated allergic reactions to study product should have his/her mechanistic blood draw and CBC ([Section 6.4](#)) at, or as soon as possible to, the time of the last dose and no later than at his or her Early Discontinuation Visit.

Home dosing symptoms during nondaily EM regimens are handled separately and discussed further in [Section 6.5.7](#).

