6.5.5.3 Dose Adjustment in Response to Intercurrent Adverse Events (QD Regimens only)

At the investigating physician's discretion, temporary dose reductions, ranging from a 1-step reduction (ie, to the previous dose) to approximately half of the current dose level (to the nearest feasible available whole dose), can be instituted as part of the treatment regimen for an intercurrent AE. Also, if a pattern of decreased tolerability of study product during menses is discerned, then a temporary dose reduction can be instituted during this time. A schematic showing procedures for temporary dose reductions due to intercurrent AEs is provided in [Figure 4](#); explanatory text follows the figure.

Figure 4: Schematic for Temporary Dose Reductions due to Intercurrent Adverse Events (QD Regimens Only)

CRC = clinical research unit; QD = daily.

- For dose reductions of ≤ 4 consecutive days, whether dose re-escalation is to occur at home or in the CRC is at the investigator's discretion. If the reduction in dose is maintained for ≤ 4 consecutive days, then the pre-reduction dose level may be resumed, with the biweekly escalation schedule kept unaltered.
- If a reduction in dose is maintained for 5 to 7 consecutive days, then the subject is to return to the CRC to undergo dosing under medical supervision. At the investigator's discretion, the pre-reduction dose level may be resumed or dosing may continue at the reduced dose level. The biweekly escalation should be reset so that the subject receives ≥ 2 consecutive weeks of treatment at the dose level assigned (either the reduced or the pre-reduction dose level).
- If a reduction in dose is maintained for 8 to 14 consecutive days, then the next escalation attempted must be conducted in the clinic, and it should only be to 1 dose level above the reduced dose. If the escalation is successful, the subject should continue home-dosing for a minimum of 2 weeks, with his or her biweekly escalation schedule reset as necessary.

Doses of study product may also be withheld at the investigator's discretion, in response to an intercurrent AE. Doses withheld as part of the treatment for an AE constitute a special category of missed peanut OIT doses ([Section 6.6](#)).

6.5.6 Treatment for Reactions During the Up-dosing Period: Pharmacological and Supportive Treatments

The treatment(s) for types of reactions during the Up-dosing period are summarized by severity of reaction in [Table 6](#).

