- If study product has been withheld for 8 to 14 consecutive days as treatment for an AE or due to a study product dispensing error, dosing may be reinitiated at approximately 25% of the last tolerated dose (to the nearest feasible available whole dose that is $\leq 25\%$ of the last tolerated dose) if the lapse in dosing occurred during the *Up-dosing Period*. If the lapse in dosing occurred during the *Maintenance Period*, (see [Figure 6](#)) dosing may, at the investigator's discretion, be reinitiated at 50% of the last tolerated dose (to the nearest feasible available whole dose that is $\leq 50\%$ of the last tolerated dose). The reduced dose is to be administered under supervision in the CRC. If tolerated, dose escalation may resume with dose increases of 1 dose level occurring no more frequently than weekly and no less frequently than every 4 weeks until the subject has returned to the dose level at which the lapse in dosing occurred. If symptoms occur, the dosing guidelines for the Up-dosing Period apply.

Figure 6: Procedures for Doses Withheld for 8 to 14 Days During the Maintenance Period

OIT = oral immunotherapy (ie, AR101, study product).

- If a subject on a QD dosing regimen has his/her study product withheld for ≥ 15 consecutive days for any reason, at any point in the study (with the exception of a dosing hiatus instituted for chronic/recurrent GI AEs at or before the 20 mg dose level, as per [Section 6.5.3.2](#)), the subject will be considered an escalation failure nonresponder, and will be asked to return to the CRC 14 days following their last dose of study product to undergo an Early Discontinuation Visit ([Section 6.3.10](#)).

During up-dosing, no attempt should be made to make up for a missed dose if greater than 6 hours have elapsed since usual time of dosing.

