7.3.3.2 Gastrointestinal Adverse Events Resulting in Prolonged Disruption of Dosing

Gastrointestinal AEs, typically chronic/recurrent GI AEs, that result in a prolonged disruption of dosing will be considered AEIs and will be assessed longitudinally according to the procedures described below. For the purpose of delineating these AEIs, prolonged

disruption of dosing is defined as withholding study product for > 7 days. This will include 3 categories of subjects:

- Any subject whose dose is withheld for > 7 days due to GI AEs and resumes dosing at a reduced dose level ([Section 7.3.3.2](#));
- Any subject who develops chronic/recurrent GI AEs at or before reaching the 20 mg dose level and resumes dosing after a 30-day dosing hiatus ([Section 6.5.3.2](#));
- Any subject who permanently discontinues dosing who had experienced a GI AE ([Section 7.3.3.2](#)).

Subjects who fall into any of these 3 categories will be asked to fill out the PEESS v2.0 questionnaire ([Franciosi et al 2011](#)), with the assistance of a parent or guardian, as appropriate, every month for 6 months. It should, however, be noted that the PEESS v2.0 was not designed to establish a diagnosis of EoE, and has not been validated for use in patients with GI symptoms of other etiologies. Furthermore, the discriminant validity of the questionnaire has not been reported in either longitudinal natural history or interventional studies. For these reasons, the use of the PEESS v2.0 to monitor the clinical course of GI symptoms must be considered exploratory. Nevertheless, the PEESS v2.0 has shown good content and construct validity ([Franciosi et al, 2011](#); [Martin et al, 2015](#)) and so holds promise for being a valuable tool to follow the clinical course of EoE or an EoE-like immune-mediated GI syndrome. Thus, the PEESS v2.0, could reveal trends toward symptomatic improvement or worsening that might otherwise go undetected.

Subjects who discontinue dosing prematurely due to chronic/recurrent GI AEs are to be requested to return to the clinic for evaluation monthly for ≥ 6 months (if the subject is asymptomatic, telephone follow-up with a physician investigator may substitute for in-clinic visit, at the investigator's discretion). If chronic/recurrent GI AEs persist beyond 6 months, subjects are to continue to be followed with monthly clinic visits until the symptoms have resolved or are assessed to have stabilized with optimal medical management.

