7.8.2 Individual Stopping Rules

Individuals may stop the study at any time by withdrawing their consent if they experience subjectively intolerable AEs, dosing symptoms, or for any other reason. Because ARC004 is exploring alternative dosing schedules, the approach to individual stopping rules caused by dose-related AEs varies by regimen. All subjects discontinuing the study early and permanently discontinuing AR101 treatment will return to the CRC for an Early Discontinuation Visit no later than 14 days after the last AR101 exposure.

QD Dosing Regimens

When on QD dosing regimens (including Up-dosing and Maintenance for Group 1, and QD EM for both Groups, as applicable), 7 or more consecutive days of missed daily dosing due to non-compliance constitutes an individual stopping rule. During Up-dosing, Group 1 subjects must halt up-dosing and re-start with a reduced dose if more than 4 days of dosing are missed. Missing 3 or more consecutive days on 3 occasions while on daily dosing in any period is an individual stopping rule, as is missing 15 or more consecutive days of QD dosing for any reason.

QOD, BIW, QW, or QOW Regimens

Any subject receiving nondaily dosing (QOD, BIW, QW, or QOW) who has 1 related SAE; 1 related AE graded severe; 2 related AEs occurring on separate occasions, both graded moderate; or 3 consecutive doses judged “not tolerated” will be considered as a treatment failure and discontinued from ARC004 for safety reasons. Such subjects may be eligible to enroll in ARC008 and receive AR101 daily in the Repeat Up-dosing period. If ARC008 is not available, the subjects will begin daily dosing and have visits in the Repeat Up-dosing period in ARC004. Once the subject reaches the target dose of 300 mg daily and maintains that dose for 2 weeks, that subject will be able to continue this dose regimen until ARC008 is available.

Occurrence of any of the following will result in the cessation of dosing and the subject being discontinued from the study as an escalation failure nonresponder:

- Failure to accomplish up-dosing of study product after 3 attempts
- Failure to identify a tolerated dose of study product after 3 attempts at dose reduction

Finally, administration of 3 or more doses of epinephrine for the treatment of any dose-related allergic reaction in any subject during any period is an individual stopping rule.

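### The 15-day missed-dose stopping rule in protocol Section 7.8.2 omits the GI-hiatus exception that Section 6.6 attaches to the same rule

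*Protocol*

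**What the plan says.** Protocol Section 7.8.2, under QD Dosing Regimens, covers Group 1 Up-dosing and Maintenance as well as daily Extended Maintenance in both groups. Its last rule for these regimens reads "as is missing 15 or more consecutive days of QD dosing for any reason". The sentence carries no exception and does not refer to Section 6.6 or 6.5.3.2.

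Five other places in the protocol bear on the same situation:

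- Section 6.6 states the 15-day, any-reason rule for daily dosing "with the exception of a dosing hiatus instituted for chronic/recurrent GI AEs at or before the 20 mg dose level", and cites 6.5.3.2.
- Section 4.3.1, item 5, has its own termination rule for more than 14 consecutive days of medically required missed dosing. It also exempts the hiatus, which it describes as lasting 30 days.
- Section 6.5.3.2, for Group 1 subjects with dose-limiting chronic or recurrent GI symptoms during Up-dosing at up to 20 mg/d, says "it is advised that dosing of study product be suspended for 4 weeks and resumed at a dose level of 3 mg/day".
- Section 6.5.5.2 lists the same step among the investigator's options: "Institute the 4-week hiatus from dosing, with resumption of dosing at the 3 mg/d dose level, as permitted for recurrent GI symptoms".
- Section 7.3.3.2 names subjects who resume after the hiatus as one of three GI follow-up categories. A separate category is "Any subject who permanently discontinues dosing who had experienced a GI AE".

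**The concern.** One rule appears twice, once with its exception and once without. The version without it is in the section headed as the individual stopping rules, to which Sections 6.5.2 and 6.5.7 send investigators. A site that acts on 7.8.2 alone would permanently discontinue a Group 1 subject partway through a suspension that the protocol itself advises.

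That subject would lose the planned restart at 3 mg and, under Section 4.3.3, would not be replaced. The subject could also be counted in the secondary safety endpoint of SAP Section 3.2 on premature discontinuation of dosing for chronic or recurrent GI adverse events, when the stop was produced by the wording of a rule. The count of GI adverse events of interest would not lose the subject, who would only move from the second category of Section 7.3.3.2 (resumes after the hiatus) to the third (stops for good).

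**Working it through.** The plan gives no figure to reproduce here. The check is a comparison of texts followed by a count of days.

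**Does the hiatus fall under the 7.8.2 rule as written?**

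1. *Period.* The 7.8.2 rules for daily regimens name Group 1 Up-dosing, which is the period of the hiatus in 6.5.3.2.
2. *Missed versus withheld.* Section 7.8.2 speaks of missing doses and Section 6.6 of withholding them. The difference does not take the hiatus outside 7.8.2, because Section 6.5.5.3 says "Doses withheld as part of the treatment for an AE constitute a special category of missed peanut OIT doses". Section 4.3.1, item 5, likewise treats the hiatus as missed dosing that needs an exemption.
3. *Reason.* In the same 7.8.2 paragraph, the 7-day rule is limited to non-compliance, whereas the 15-day rule applies whatever the reason. The contrast brings withholding for an adverse event within the 15-day rule.
4. *Carry-over of the exception.* The note in 6.5.3.2 makes the hiatus an exception to the rules in Section 6.6 and does not name 7.8.2. Section 7.8.1 introduces the Section 7.8 rules as additional to the criteria in 4.3.1, so the exemption in 4.3.1 does not reach 7.8.2 by its terms.

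Section 7.8.2 drops another qualifier as well. Section 6.6 excludes treatment of an adverse event from its rule on three occasions of 3 consecutive missed days; 7.8.2 states that rule without the exclusion. This suggests that qualifiers were lost when the rules were restated.

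**Days left when the rule is first met**

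Days left = length of hiatus − 15.

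- 4-week hiatus (6.5.3.2, 6.5.5.2): 4 × 7 = 28 days; 28 − 15 = **13 days left**.
- 30-day hiatus (4.3.1, 7.3.3.2): 30 − 15 = **15 days left**.

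**Where the conflict can arise**

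- Group: Group 1 only, planned size 130 (Section 7.8.3).
- Dose levels: Section 3.1.2 describes dosing as "starting at a dose of 3 mg once daily and gradually escalating every 2 weeks to a maximum of 300 mg once daily". Table 2 has 11 levels, of which 3, 6, 12 and 20 mg are at or below 20 mg: 4 of 11.
- Scheduled time: 4 × 2 = 8 weeks, out of 11 × 2 = 22 scheduled weeks. Holds and dose reductions can stretch Up-dosing to 40 weeks, so a particular subject may still be at or below 20 mg after week 8.

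The documents do not support a reliable estimate of how many subjects would take the hiatus, so none is given.

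**After the correction.** With the 6.6 exception added, the 15-day rule no longer applies to the hiatus and both gaps disappear.

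**The case against.** The strongest reply is that the protocol already settles the matter. Section 6.6 gives the fuller form of the rule with the exception attached; 6.5.3.2 and 6.5.5.2 direct or permit the hiatus; 4.3.1 exempts it; and 7.3.3.2 and the Appendix 1 schedule footnotes provide follow-up for subjects who resume afterwards. A site starting a GI hiatus would be working from 6.5.3.2, which points to 6.6. The sentence in 6.5.5.3 that classes withheld doses as missed also cross-refers to 6.6. The specific provision should govern the general one, and a Medical Monitor is available for questions. The SAP makes no formal comparisons (Section 6.4), so no inference depends on this.

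Most of that stands. The intent is plain, a careful reader would probably follow 6.6, and the number of subjects affected may be zero. Two qualifications are also fair: the gap is 15 days on the 30-day wording, and the 8-week window holds only for the scheduled course.

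None of this supplies the missing words. Section 7.8.2 is an operative rule that, as written, gives the wrong instruction, and nothing in it directs the reader to the exception. That the intent is clear elsewhere makes the point minor without making the text correct.

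**Conclusion.** The point holds as a minor internal inconsistency. Read literally, Section 7.8.2 requires discontinuation on missed day 15 of the 28-day hiatus that Section 6.5.3.2 advises, 13 days before it ends. The conflict is confined to Group 1 subjects at 3, 6, 12 or 20 mg. It poses no threat to the study's conclusions; the possible harm is the wrongful discontinuation of individual subjects and their misplacement in one descriptive safety endpoint.

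This rests on two readings: that doses withheld for the hiatus count as missed doses, which 6.5.5.3 and 4.3.1 support, and that a site applies 7.8.2 without reading 6.6 into it. The 14-day limit on withholding in Section 6.5.5 is a separate matter. It concerns intercurrent adverse events and checks of tolerability, and is not taken here to end the hiatus.

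**What to change.** In Section 7.8.2, at the end of the 15-day rule, add the exception from Section 6.6, "with the exception of a dosing hiatus instituted for chronic/recurrent GI AEs at or before the 20 mg dose level", with a reference to Section 6.5.3.2. A matching cross-reference at the 14-day withholding bullet in Section 6.5.5 is optional and for consistency only.

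The cost is one phrase in the protocol, plus the optional cross-reference. Data collection, sample size and analysis are unaffected.

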7.8.3 Cohort Stopping Rules

ARC004 will consecutively enroll eligible subjects into different cohorts, each of which will produce evidence during the trial concerning the feasibility and safety of adjusting EM dosing from daily to a less frequent schedule. The information that becomes available as each cohort proceeds through the study will be evaluated before determining whether the next cohort is to advance to a longer interval between doses. No subject will be exposed to a regimen with longer dosing intervals (eg, QOD to BIW, BIW to QW, or QW to QOW) if evidence from the previous cohorts suggests that doing so would more likely than not cause subjects at the new interval to either experience more frequent or more severe AEs, or lose desensitization that they may have gained/maintained, had they remained on more frequent dosing. Because they will have had 28 additional weeks of QD maintenance, Cohorts 3B and 3C will be allowed to proceed to QOD and BIW dosing independent of Cohort 2's experience according to the judgment of the Safety Monitoring Committee (SMC).

For each cohort, all subjects discontinuing early due to AEs (eg, dropouts) will be considered failures. Likewise, subjects who lose protection during their ARC004 Exit DBPCFC, when compared either to their ARC003 Exit DBPCFC (Group 2), or their ARC004 Post-Maintenance DBPCFC (Group 1) will be considered failures (eg, failed completers), as follows:

- Subjects tolerating 443 mg at the previous DBPCFC must tolerate ≥ 443 mg at the ARC004 Exit DBPCFC, or be considered a failure
- Subjects tolerating 1043 mg at the previous DBPCFC must tolerate ≥ 443 mg at the ARC004 Exit DBPCFC, or be considered a failure
- Subjects tolerating 2043 mg (or greater, for Group 1 subjects) at the previous DBPCFC must tolerate ≥ 1043 mg at the ARC004 Exit DBPCFC, or be considered a treatment failure

The treatment failure rate in each cohort will be monitored on an ongoing basis by the SMC, and calculated according to the following formula:

Treatment failure rate = [(dropouts) + (failed completers)] / planned size* for the cohort

Whenever this number is greater than 50%, then this stopping rule is met and further prolongation of the dosing interval in any subsequent cohort will cease. As an additional safety precaution, if individual stopping rules (eg, due to AEs) are invoked in 10 of the first 20 subjects to enroll in any cohort, further enrollment in that cohort will cease. Finally, the SMC retains the authority to stop further enrollment into a cohort at any time for any reason. If any of these conditions transpire, all remaining subjects, including those ongoing subjects in the terminated cohort, and future subjects, will be administered AR101 300 mg at the longest interval tolerated by a previous cohort.

*Assumptions = Up to approximately 500 ARC003 completers (having received active or placebo in ARC003 at a 3:1 ratio) are projected for recruitment into ARC004. This assumes a loss of 15% of the randomized ARC003 population due to attrition, AEs, etc. Thus, the planned sizes for the ARC004 cohorts is as follows, though the actual number may vary due to recruitment:

- Cohort 1 = 120, prespecified
- Cohort 2 = 50, prespecified
- Cohort 3 = 175, distributed equally across Cohorts 3A, 3B, 3C
- Group 1 = 130 (25% of ARC003 enrollment, accounting for 5% dropout)

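### The cohort stopping rule in 7.8.3 divides failures by planned size, so for Cohort 3 and Group 1 it is a fixed failure count that equals the stated 50% only if enrolment meets plan

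*Protocol*

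**What the plan says.** Protocol Section 7.8.3 has the SMC monitor, for each cohort, "Treatment failure rate = [(dropouts) + (failed completers)] / planned size* for the cohort". Dropouts are subjects who discontinue early because of adverse events. Failed completers are those who lose protection at the Exit DBPCFC relative to their previous challenge. Above 50%, "further prolongation of the dosing interval in any subsequent cohort will cease". The section adds that all remaining subjects, including those still on treatment in the cohort that met the rule, go to the longest dosing interval an earlier cohort has tolerated.

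The asterisk leads to a list of planned sizes: 120 for Cohort 1, 50 for Cohort 2, "Cohort 3 = 175, distributed equally across Cohorts 3A, 3B, 3C", and 130 for Group 1. The list is introduced with the caveat "though the actual number may vary due to recruitment".

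Cohorts 1 and 2 have set numbers. Section 3 makes Cohort 3 open-ended: whoever enters Group 2 from the 171st subject on. Group 1 depends on how many ARC003 placebo completers roll over.

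The synopsis expresses the same rule as failures in more than half of any cohort, does not mention planned size, and points to 7.8.3. The SAP defines no treatment failure rate.

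**The concern.** A threshold stated as a percentage should mean the same proportion of treated subjects however recruitment turns out. With planned size as a permanent denominator, the rule becomes a set number of failures. If a cohort under-enrols, more than half of its subjects must fail before the rule is met; if it over-enrols, the rule is met below half. In an arm with fewer than 30 subjects it could never be met.

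The rule decides whether later cohorts lengthen their interval and whether subjects already on a long interval are moved back. It bears mainly on Cohorts 3B and 3C, because 3A is daily throughout. Group 1 is also affected: no cohort follows it, but its own ongoing subjects would revert.

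The footnote also leaves the unit open. It gives one size for Cohort 3 and does not say whether the denominator is 175 or one third of it.

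**Working it through.** **Inputs.** Planned sizes and the 50% trigger are from Protocol 7.8.3. The total of up to about 500 rollovers is from the same footnote. The total of about 400 (80% of 500) is from Protocol 9.4. The 3:1 ratio is ARC003's allocation; applying it exactly to rollovers is an assumption.

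**Trigger counts as written.** The smallest count above 50% is floor(planned/2) + 1.

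- Cohort 1: 61 of 120 = 50.8%. Cohort 2: 26 of 50 = 52.0%.
- Cohort 3 per arm: 175/3 = 58.33. 29/58.33 = 49.7% and 30/58.33 = 51.4%, so the trigger is 30.
- Cohort 3 pooled: 88/175 = 50.3%.
- Group 1: 66/130 = 50.8%.

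At plan, then, the rule does what it says.

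**Does the plan hold together?** Back-solving with the footnote's losses gives an ARC003 size of 345/(0.75 × 0.85) = 541 from the Group 2 total (120 + 50 + 175 = 345), and 130/(0.25 × 0.95) = 547 from Group 1. Taking 545 (an inference; Protocol 9.4 gives a target of 500), an arm has (0.75 × 545 × 0.85 − 170)/3 = 59.1 subjects and Group 1 has 0.25 × 545 × 0.95 = 129.4. Triggers based on enrolled size would be 30 of 59 and 65 of 129, a gap of 0 and 1 failures.

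**Away from plan.** Arm size = (0.75 × total − 170)/3 and Group 1 = 0.25 × total. For the ARC003 = 500 row, 15% active and 5% placebo loss are assumed: (375 × 0.85 − 170)/3 and 125 × 0.95.

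| Scenario | Arm size | 30/arm size | Enrolled-size trigger | Group 1 size | 66/Group 1 size | Enrolled-size trigger |
|---|---|---|---|---|---|---|
| 400 rollovers | 43.3 | 69.2% | 22 | 100 | 66.0% | 51 |
| ARC003 = 500 with losses | 49.6 | 60.5% | 25–26 (arm of 49–50) | 118.75 | 55.6% | 60 |
| 500 rollovers | 68.3 | 43.9% | 35 | 125 | 52.8% | 63 |

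At 400 rollovers the fixed count needs 8 extra failures per arm (30 − 22) and 15 extra in Group 1 (66 − 51). At 500 it is met 5 failures early per arm (35 − 30) and 3 late in Group 1 (66 − 63). Pooled over Cohort 3, the shares are 88/130 = 67.7% and 88/205 = 42.9%.

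**Sensitivity to the mix.** Holding Group 1 at 130, the per-arm share is 30/(100/3) = 90% at 400 and 30/(200/3) = 45% at 500. With the planned 345:130 mix it is 75% and 47%.

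**Effect on the decision (illustration).** If the true failure probability were 60%, a 43-subject arm would meet a fixed count of 30 with binomial probability 12%, and an enrolled-size count of 22 with probability 91%.

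**Pooled or per arm.** On the pooled reading at planned size, if 3A (daily) fails in 0% to 20% (assumption), 3B and 3C together (116.7 subjects) need 88/116.7 = 75% down to (88 − 11.7)/116.7 = 65% failures.

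**The case against.** A fixed denominator is a legitimate choice for a rate watched continuously. It gives a known count and cannot be met by a handful of early failures; an enrolled-size denominator would be met at 2 of the first 3. That stands, and it is why planned size should be kept during enrolment. No figure in the protocol is miscalculated.

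An SMC could take the recruitment caveat and the synopsis wording together and use actual size. It could, but the only formula given says planned size and nothing instructs the switch.

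The rule is also not the only gate, which limits the harm:

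- Section 3.1.5 requires an SMC recommendation before a cohort lengthens its interval, and SMC approval of Group 2 data before Group 1 changes.
- Section 7.8.3 bars a longer interval if the experience gained so far "suggests that doing so would more likely than not cause subjects at the new interval to either experience more frequent or more severe AEs". The same clause covers a loss of protection. That test has no denominator.
- Subjects in 3B reach their exit challenge at about Week 56, when 3C subjects randomized at the same time are due to start weekly dosing. Many 3B challenge results therefore could not inform that step under any denominator.

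These are matters of judgment or timing and do not correct the formula. The early numeric rule does not replace it either: it acts when individual stopping rules are invoked in "10 of the first 20 subjects to enroll in any cohort, further enrollment in that cohort will cease". It does not count failed completers, so loss of protection at the exit challenge enters a numeric rule only through the 50% formula.

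**Conclusion.** The concern holds as a wrong decision threshold with bounded consequences. As written, the rule is 30 failures per Cohort 3 arm (88 if pooled) and 66 in Group 1. It matches the stated 50% only when those cohorts reach plan, where the gap is 0 to 1 failures. Cohorts 1 and 2 are unaffected if filled.

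Three stronger readings are not supported.

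- A reader might take 44% to 69% per arm as the limits of the error. They are two scenarios under an assumed exact 3:1 mix. The 400 in Section 9.4 is an accrual assumption used for rare-event detection, not a lower bound, and other mixes give other figures.
- A reader might infer that the rule let unsafe lengthening proceed. The documents do not show that. SAP Section 2.3 reports that, on SMC advice, subjects in 3C on twice-weekly dosing and Group 1 subjects on daily dosing stayed there, with no specific safety signal. SAP Section 6.1 says no one began weekly or every-other-week dosing.
- A reader might infer that Group 1 is untouched because no cohort follows it. The reversion of ongoing subjects in 7.8.3 says otherwise.

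The 50% threshold itself is not in question. This is a correction worth making, at low priority.

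**What to change.** In 7.8.3, keep planned size as the denominator while a cohort is enrolling. Once its enrolment closes, divide by the smaller of planned and enrolled size. In the footnote, state that the rule applies to 3A, 3B and 3C separately. In the synopsis, use the same definition.

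At 400 rollovers the final triggers would be 22 of 43 per arm and 51 of 100 in Group 1. At 500 rollovers an arm's trigger would stay at 30 and Group 1's would be 63 of 125. Under-enrolment could then no longer raise the threshold beyond integer rounding. Over-enrolment would not loosen a safety rule, as it would if enrolled size alone were used (35 instead of 30 per arm at 500 rollovers).

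The cost is a line in 7.8.3, a sentence in the footnote and a phrase in the synopsis. The trigger count becomes final only when enrolment closes, and an over-enrolled arm is held to less than 50% (44% at 500 rollovers), which errs on the cautious side.
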